1. INTRODUCTION

Cerebral palsy (CP) is a heterogeneous condition due to injury to the developing brain. It is a condition that is often marked by both cognitive and motor disorders as well as increased prevalence of depression and anxiety. While most studies have focused on improving motor dysfunction, fewer have investigated cognitive impairments associated with CP. Dedicating a study to research the pharmacotherapeutic effect of Amantadine on cognitive function in adolescents and adults with cerebral palsy fills an important gap in development of a potential innovative treatment for cognitive deficits.

This study's approach to treatment is aimed at improvement of cognitive function in primarily the adolescent and adult CP population, something that has not been wholly addressed by the research community to date. In the rehabilitation outpatient setting, we have used Amantadine in children and adults with CP for its dopaminergic properties. Amantadine, initially used as an anti-viral drug, is well supported in the literature for its efficacy in treating acute traumatic brain injury (TBI) to improve alertness, arousal, consciousness, mobility and improve rate of recovery. Based on the success of Amantadine in the TBI population, there are implications for its use in the cerebral palsy population because of the similar etiology of brain injury, but in the developing brain. The aim of this study is to determine the effects of Amantadine in primarily adolescents and adults with CP and to compare pre- and post-intervention outcomes related to the primary goal of improving cognitive function, focused on processing speed and attention span. We will also evaluate secondary goals of improving gross and fine motor skills as well as change in mood since Amantadine controls rigidity that could help functional mobility

2. DESIGN

This single center, prospective, open label study will enroll adolescents and adults diagnosed with cerebral palsy, aged 13-65 years, and case-by-case assessment for children under the age of 13 years old, with a target sample size of 10 participants. A baseline assessment of the following domains will be conducted: cognitive function, gross motor & fine motor function, and mood/psycho-social function. Participants will start a daily regimen of Amantadine: dosing 2-5 mg/kg divided by two daily doses (max daily dose of 300 mg). Participants and caregivers will be given a diary to document their perceived effects of Amantadine.

At 3 and 6 weeks, we will repeat the assessments done in the pre-test to evaluate the efficacy of Amantadine. See below for assessment tools, performed as able according to participants' functional status:

1. Cognitive function: NIH Toolbox (Cognitive Battery)
2. Mood: Patient Health Questionnaire-9 (PHQ-9), BRIEF-A
3. Gross motor function: Berg Balance Test, Timed Up and Go, Modified Ashworth Scale, Modified Tradieu Scale, Passive Range of Motion
4. Fine motor function: Box and Blocks
5. Subjective self-assessment: Patient self-assessment of changes in attention, processing and motor skills

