2.1 Participants

This single center, prospective, open label study will enroll adults diagnosed with cerebral palsy aged 13 to 65 years, including a case-by-case basis of including those under the age of 13 years old, with a target sample size of 10 participants.

Most subjects will be recruited from [name] Medicine & Rehabilitation clinic. [name] will approach eligible patients in order to explain the study and to determine interest. Other physicians will also approach eligible patients and will explain the study. A brochure/flyer will be presented to each eligible and interested patient, with the study team's contact information on it for their reference. If they are interested and eligible right away, patients will be asked to fill out the consent form and provide us with their contact information so that we can contact them to schedule their initial assessment visit. Other recruitment methods include use of brochures/flyers in other departments in the hospital/CP Center. There will be no screening over the phone or via email.

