2.2 Outcome Measures

Primary Question: Does Amantadine have an effect on cognitive function in 10 adolescents and adults diagnosed with cerebral palsy (CP)?

Hypothesis: If 10 adolescents and adults receive Amantadine, then cognitive function will increase/improve.

Secondary Question: Does Amantadine have an effect on fine and gross motor skills, and mood?

Hypothesis: If 10 adolescents and adults receive Amantadine, then there will be increased fine and gross motor skill function and improved rigidity, and mood scores will improve on the PHQ-9.

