2.4 Statistical Analysis

No power calculations were made since there is no previous study that used the same population (adolescents and adults), with the same intervention (Amantadine), to find the same outcomes (cognitive and motor function).

The results will be statistically analyzed by using the paired samples t-test on SPSS.

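### Does letting children under 13 take places within the target of 10 leave the plan without a usable analysis population?

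*Combined protocol and SAP*

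**What the plan says.** Section 2 (Design) enrols ages 13 to 65 and adds "case-by-case assessment for children under the age of 13 years old, with a target sample size of 10 participants". Section 2.1 (Participants) repeats the point: "including a case-by-case basis of including those under the age of 13 years old". Neither section sets a maximum for children or gives them extra places, so they count within the 10.

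Section 2.2 (Outcome Measures) is narrower. The primary question is "Does Amantadine have an effect on cognitive function in 10 adolescents and adults diagnosed with cerebral palsy (CP", the primary hypothesis is "If 10 adolescents and adults receive Amantadine, then cognitive function will increase/improve", and the secondary hypothesis begins "If 10 adolescents and adults receive Amantadine, then there will be increased fine and gross motor skill function and improved rigidity". The secondary question names no population.

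Section 2.4 (Statistical Analysis) explains that no power calculation was made because "there is no previous study that used the same population (adolescents and adults" with the same intervention and outcomes. Its analysis plan is one sentence: "The results will be statistically analyzed by using the paired samples t-test on SPSS". It states no analysis set and no age rule.

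The Introduction is looser than section 2.2. It describes the treatment approach as aimed at "improvement of cognitive function in primarily the adolescent and adult CP population", and it uses the same qualifier, primarily, when stating the study aim.

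**The concern.** The people who may be enrolled and the people named in the hypotheses are not the same group. If k children under 13 enter within the 10, only 10 − k participants aged 13 to 65 remain, so the hypotheses hold as worded only when k = 0.

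There are two possible consequences. If the children are left out, the 13-to-65 comparison has fewer than ten people. If they are included, each child who supplies data on an outcome carries up to one tenth of the weight in a comparison described as concerning adolescents and adults. Because no analysis set is written down, the choice could in principle be made after an unblinded team has seen the data. In a study of ten, one or two people can matter.

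**Working it through.** **Comparing the sections.** Sections 2 and 2.1 count children within the 10. The Introduction foresees some children. Section 2.4 applies its method to the results without excluding anyone. These four places agree on one reading: all enrolled participants are analysed. The narrower wording in section 2.2 and in section 2.4's reason for omitting a power calculation is shorthand that drops the qualifier used in the Introduction. Admission of children is by exception, no number is planned, and k = 0 also fits the text.

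**Plan's own figure.** The target of 10 does not come from a power calculation, so there is no power or precision figure to reproduce.

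**Inputs.** The target of 10 is from section 2. Everything else is assumed: k = 1 to 3 children; a difference d = 0.5 to 1.0 between their mean change and that of ages 13 to 65; an SD of change of 1 in both groups; two-sided 5% tests; complete data on the outcome.

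**If children are left out (n = 10 − k).** The 95% half-width is t(0.975, n−1)/√n. The change detectable with 80% power comes from the noncentral t distribution.

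| n | Half-width (SD) | Detectable change (SD) |
|---|---|---|
| 10 | 0.72 | 1.00 |
| 9 | 0.77 | 1.07 |
| 8 | 0.84 | 1.16 |
| 7 | 0.92 | 1.27 |

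**If children are pooled (n = 10).** The shift from the 13-to-65 mean is kd/10. The standard error the analyst would see is √[(1 + d²k(10−k)/90)/10]. For k = 3, d = 1.0 the shift is 0.30 and the standard error is √[(1 + 21/90)/10] = 0.351, a ratio of 0.85. For k = 1, d = 0.5 they are 0.05 and 0.320, a ratio of 0.16. The other cases lie between. Coverage of the 13-to-65 mean by the pooled 95% interval, from 400,000 simulated trials per case, is shown below.

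| | k = 1 | k = 2 | k = 3 |
|---|---|---|---|
| d = 0.5 | 95.0% | 94.5% | 93.6% |
| d = 1.0 | 95.0% | 93.4% | 90.2% |

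**Which choice estimates the 13-to-65 mean better?** Mean squared error is 1/10 + (kd/10)² when pooled and 1/(10 − k) when restricted.

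| k | d | Pooled | Restricted | Smaller |
|---|---|---|---|---|
| 1 | 0.5 | 0.1 + 0.0025 = 0.1025 | 1/9 = 0.111 | pooled |
| 1 | 1.0 | 0.1 + 0.01 = 0.110 | 0.111 | pooled |
| 2 | 0.5 | 0.1 + 0.01 = 0.110 | 1/8 = 0.125 | pooled |
| 2 | 1.0 | 0.1 + 0.04 = 0.140 | 0.125 | restricted |
| 3 | 0.5 | 0.1 + 0.0225 = 0.1225 | 1/7 = 0.143 | pooled |
| 3 | 1.0 | 0.1 + 0.09 = 0.190 | 0.143 | restricted |

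The two are equal when d² = 10/[k(10 − k)], that is at d = 1.05, 0.79 and 0.69 for k = 1, 2 and 3. Restriction helps only above those values.

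**The case for a change.** The strongest case for acting is that the mismatch is certain, needs no outside assumption and would take only a few sentences to remove. With so few participants and no blinding, a written analysis set guards against choosing it after the results are known. A reader of the report should also be able to tell whom the t-tests describe.

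The textual mismatch stands, and so does the general principle. What does not follow is a gain from changing the plan. Each available change can be weighed in turn:

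- **Rewording sections 2.2 and 2.4 to cover all enrolled ages** writes down what the ordinary reading already gives and alters no result.
- **Requiring all ten places to be filled by ages 13 to 65** means extra or slower recruitment at one centre, against the evident choice in sections 2 and 2.1 to count children within the target.
- **Restricting the primary set within the 10** costs precision and, on the assumptions above, more often raises the mean squared error than lowers it.
- **A cap on children and written admission criteria** would add detail, but nothing in the planned analysis depends on them.

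It would also overstate the problem to say that a single test hangs on this choice. Section 2.4 names one method, while section 2 lists many instruments repeated at 3 and 6 weeks and given as participants are able. A child's weight will therefore differ by outcome and may be nil for some.

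**Conclusion.** The inconsistency in wording is real but does not call for a change. The sections on enrolment, the Introduction and the unrestricted sentence in section 2.4 together support analysing everyone enrolled, and an analyst would do that and report the ages of those included.

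The likely effect is small. With one child, pooling leaves coverage at 95.0%. With three children it falls to 93.6% at d = 0.5 and 90.2% at d = 1.0. The shift stays below one standard error throughout. Leaving one child out instead widens the half-width from 0.72 to 0.77 SD, which would not alter how an uncontrolled before-after study of ten people is read.

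These figures rest on assumed values of k and d and a common SD of change, none of which the documents give. The conclusion would weaken if several children were enrolled and responded very differently: restriction has the smaller error for k = 2 or 3 at d = 1.0. Nothing in the plan suggests that this is expected.

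### The plan asks whether amantadine works, but with no comparator and one baseline a paired t-test can show only total change on treatment

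*Combined protocol and SAP*

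**What the plan says.** The stated purpose is causal in several places.

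- Section 1 presents the work as follows: "Dedicating a study to research the pharmacotherapeutic effect of Amantadine on cognitive function in adolescents and adults with cerebral palsy". It then gives the aim: "The aim of this study is to determine the effects of Amantadine in primarily adolescents and adults with CP".
- Section 2 says of the follow-up visits: "At 3 and 6 weeks, we will repeat the assessments done in the pre-test to evaluate the efficacy of Amantadine". Section 2.3 repeats this almost word for word.
- The secondary question in section 2.2 is "Does Amantadine have an effect on fine and gross motor skills, and mood", and the primary question has the same form for cognition. The primary hypothesis reads: "If 10 adolescents and adults receive Amantadine, then cognitive function will increase/improve".

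The design and analysis are simpler than that purpose.

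- Section 2 states: "This single center, prospective, open label study will enroll adolescents and adults diagnosed with cerebral palsy". Section 2.1 also calls the study open label. The target is 10 participants.
- Sections 2 and 2.3 describe one baseline assessment, after which participants start amantadine. The same assessments follow at 3 and 6 weeks.
- Section 2.4 names a paired samples t-test and nothing else.

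Section 1 also describes a narrower task: "to compare pre- and post-intervention outcomes related to the primary goal of improving cognitive function". The paired t-test can do that.

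**The concern.** The question and the estimator do not match. The plan asks about the effect of a drug, but the quantity it will estimate is mean change from before to after. The two are equal only if nothing else moves the scores over six weeks, and the plan neither assumes nor defends that.

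Features of the plan make other sources of change plausible. The same cognitive battery is given up to three times in six weeks. Mood and self-assessed change are reported by people who know they are taking the drug, and the diary asks for its perceived effects.

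The supplied text describes no concurrent or historical control, repeated baseline, run-in, withdrawal period or correction for practice. Nothing in it limits how a result will be read or calls the study exploratory. Taken at its word, the plan would let a significant paired t-test stand as a positive answer on efficacy. It would equally let a null result stand as a negative answer, although unfavourable non-drug change could have hidden a benefit.

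**Working it through.** **What the test estimates.** For one outcome and one follow-up visit:

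E(post − pre) = drug effect + retest effect + expectancy + other time-related change.

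The paired t-test has the null hypothesis that this sum is zero. With every participant treated and one pre-dose score, there is one estimable quantity and several unknowns. This is a failure of identification, not of precision.

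**No stated figure to reproduce.** Section 2.4 says no power calculation was made. The documents give no alpha, sidedness, effect size, SD or retest correlation.

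**Illustration.** Only n = 10 comes from the documents (the target sample size, taken here as 10 complete pairs). Assumptions: two-sided alpha 0.05, equal SD before and after, retest correlation r, drug effect zero, and a non-drug gain m in baseline SD units.

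- Standardised change: dz = (drug + m)/√(2(1 − r)).
- Noncentrality: dz × √n. Critical value with 9 df: 2.262.
- Probability of a significant improvement: upper tail of the noncentral t beyond 2.262. With no change of any kind this is 0.025.

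For r = 0.8, √(2 × 0.2) = 0.632:

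| m (SD) | dz | noncentrality, n = 10 | n = 10 | n = 20 | n = 40 |
|---|---|---|---|---|---|
| 0.2 | 0.316 | 1.00 | 0.144 | 0.269 | 0.496 |
| 0.3 | 0.474 | 1.50 | 0.269 | 0.521 | 0.833 |
| 0.5 | 0.791 | 2.50 | 0.606 | 0.918 | 0.998 |

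A simulation of 200,000 trials agreed to within 0.001. Nobody proposes 20 or 40 pairs; those columns show only that a larger sample does not remove the problem and makes a false attribution more likely.

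Sensitivity to r, with n = 10:

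| m (SD) | r = 0.5 | r = 0.7 | r = 0.9 |
|---|---|---|---|
| 0.2 | 0.082 | 0.110 | 0.244 |
| 0.3 | 0.134 | 0.194 | 0.474 |
| 0.5 | 0.293 | 0.446 | 0.881 |

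Smaller or opposite changes at r = 0.8 and n = 10: a gain of 0.1 SD gives 0.065; a decline of 0.2 SD gives 0.002.

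**Only the sum matters.** Drug and non-drug gains of 0.3 and 0, 0 and 0.3, or 0.15 and 0.15 all give dz = 0.3/0.632 = 0.474 and the same probability, 0.269. A fully active drug, an inert one and a half-and-half case produce the same distribution of results.

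**The case against.** The strongest reply is that an uncontrolled before-and-after study is a reasonable first step with 10 participants, and that this one does not hide its nature: it says open label and speaks of pre- and post-intervention comparison. It has no success criterion or decision rule, so no efficacy claim is formally triggered. Because the remedy changes no observation and no p-value, it could be called editorial.

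Much of this is fair. The design is acceptable for a small early study, and this point does not ask for a control arm. The root cause is the missing comparator; open label adds expectancy but would not by itself prevent attribution. The hypothesis in section 2.2, read alone, predicts only improvement on treatment. A null result from 10 participants would be weak even in a controlled trial. The illustrative figures rest on assumed inputs and are low when the non-drug change is small or negative.

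None of this removes the mismatch. The efficacy purpose is explicit without a decision rule. The hypothesis sits directly under a question about the drug's effect. Nothing in the supplied text tells a reader that the result is to be taken as change only. The wording of the question decides what a p-value below 0.05 will be taken to mean.

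**Conclusion.** The concern holds and should be corrected before the results are interpreted. The plan poses a causal primary question that its design and analysis cannot answer in either direction. The conclusion follows from the structure alone: one treated group, one baseline and a test of mean change. It needs no assumed figure.

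The size of the consequence is unknown, because the documents give neither the size nor the direction of non-drug change. Under the stated assumptions, with 10 pairs, correlation 0.7 to 0.9 and no drug effect, non-drug gains of 0.2, 0.3 and 0.5 SD give a significant improvement in 11–24%, 19–47% and 45–88% of trials. The nominal 5% level protects against a false finding of change, not against a false finding of drug effect.

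**What to change.** Change the wording in five sections.

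1. **Sections 2 and 2.3:** replace the statement that the repeat assessments evaluate efficacy with: *describe change on open-label Amantadine*.
2. **Section 1:** replace the reference to researching a pharmacotherapeutic effect on cognition with: *describe change in cognitive function on open-label Amantadine*. Restate the aim of determining effects as: *describe change on open-label Amantadine*. Keep the phrase about comparing pre- and post-intervention outcomes.
3. **Section 2.2, primary question:** *Does cognitive function change from baseline at the planned 3- and 6-week assessments in 10 adolescents and adults with CP on open-label Amantadine?* **Hypothesis:** *Cognitive function will improve from baseline at these assessments on open-label Amantadine.* Restate the secondary question and hypothesis in the same way for motor skills, rigidity and mood. This text does not choose between the two time points, which the plan also leaves open.
4. **Section 2.4, add:** *The paired t-test assesses mean change from baseline on open-label Amantadine, which includes any retest, expectancy and other time-related effects. Results are preliminary; a change, or its absence, will not be attributed to the drug alone.*

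Visits, data, sample size and test are unchanged. The cost is a less favourable stated claim. If the sponsor wants to keep the efficacy question, the design itself would have to change, for example by adding a comparator; rewording would not be enough.

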2.3 Procedures

A baseline assessment of the following domains will be conducted: cognitive function, gross motor and fine motor function, and mood/psycho-social function. Because the PHQ9 assessment asks a question regarding suicide ideality, we will promptly review it each time it is completed, and if suicide ideality is reported, the subject will be provided with appropriate resources.

Participants will start a daily regimen of Amantadine: dosing of 2-5 mg/kg divided by two daily doses (max daily dose of 300 mg). Participants and caregivers will be given a diary to document their perceived effects of Amantadine. At 3 and 6 weeks, we will repeat the assessments done in the pre-test to evaluate efficacy of Amantadine.

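### Does a self-rating of change, listed among the repeated assessments, leave the paired t-test with nothing to compare?

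*Combined protocol and SAP*

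**What the plan says.** Section 2 (DESIGN) of the combined protocol and SAP gives the baseline content first: "A baseline assessment of the following domains will be conducted: cognitive function, gross motor & fine motor function, and mood/psycho-social function". It then sets the repeat schedule: "At 3 and 6 weeks, we will repeat the assessments done in the pre-test to evaluate the efficacy of Amantadine". A separate sentence introduces the instruments: "See below for assessment tools, performed as able according to participants' functional status". Five tools follow, covering cognition, mood, gross motor function, fine motor function and, fifth, a "Patient self-assessment of changes in attention, processing and motor skills".

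Section 2.3 (Procedures) gives the same baseline domains and the same repeat rule: "At 3 and 6 weeks, we will repeat the assessments done in the pre-test to evaluate efficacy of Amantadine".

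Section 1 (INTRODUCTION) states the aim, which is to "compare pre- and post-intervention outcomes related to the primary goal of improving cognitive function, focused on processing speed and attention span". The primary question in section 2.2 concerns cognitive function. The secondary question reads: "Does Amantadine have an effect on fine and gross motor skills, and mood". Neither question nor its hypothesis mentions the self-assessment.

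Section 2.4 gives the whole analysis in one sentence: "The results will be statistically analyzed by using the paired samples t-test on SPSS". It names no pair of visits, no score and no tool.

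The documents give no scale, recall period, visit schedule or separate analysis for the self-assessment.

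**The concern.** The first four tools record a participant's state on the day, so a value before treatment and a value at week 3 or week 6 can be subtracted. The fifth is worded as a rating of change. Before the first dose there is no change on treatment to rate. If the repeat rule covers all five tools and the paired t-test covers all results, the plan seems to call for a difference with one side undefined.

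Two things would be at stake. The tool asks about attention and processing, which the Introduction names as the focus of the primary goal, so a reader could set its result beside the NIH Toolbox result. There is also a possible loss of data: if current status is what the investigators want but the form asks about change, the pre-treatment state is never recorded and no later analysis can recover it.

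**Working it through.** The plan gives no power, effect size or standard deviation, so there is no figure of its own to reproduce. The check is mainly a reading of the text.

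**Step 1. Which tools are pre-test assessments?** The repeat rule reaches only what was done at the pre-test.

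| Tool | Content | In the baseline list of sections 2 and 2.3? |
|---|---|---|
| 1 | Cognition | Yes |
| 2 | Mood | Yes |
| 3 | Gross motor | Yes |
| 4 | Fine motor | Yes |
| 5 | Self-assessment of change | Not named |

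The idea that tool 5 is repeated from the pre-test comes from its place in the list. The text does not say so. Equally, no tool is marked as post-baseline only, so the baseline list favours one reading without settling it.

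**Step 2. What happens under each reading?**

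- *(a) Change rated at weeks 3 and 6 only.* There is no baseline value to pair, and none is needed, because the comparison with the start of treatment is already in the answer. The analyst counts improved, unchanged and worse, or tests the mean against no change. A week 3 versus week 6 pair exists but would not test change from baseline.
- *(b) Current status rated at all three visits.* The word *changes* is loose, and the paired test applies as written.
- *(c) Change rated before treatment as well, then subtracted.* This is the literal reading of list position plus section 2.4. It requires participants to rate change over some unstated period before the drug.

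**Step 3. How precise could tool 5 be under (a)?** As an illustration, suppose 7 of 10 report improvement. The exact (Clopper-Pearson) 95% limits are the 2.5% quantile of Beta(7, 4), which is 0.348, and the 97.5% quantile of Beta(8, 3), which is 0.933. An interval of 35% to 93% supports description and little more.

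**Step 4. How bad could (c) be?** All inputs here are assumptions except n = 10: a normally distributed rating with 0 meaning no change, week-6 mean 1.2, SD 1.25, two-sided 5% level. Power comes from the noncentral t distribution with 9 degrees of freedom and noncentrality (mean difference) / (SD of difference / √10).

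- If everyone answers 0 at the pre-test, the subtraction does nothing. Noncentrality is 1.2 / (1.25 / √10) = 3.04 and power is 0.77, the same as a one-sample test against 0.
- If pre-test answers average 0.5 with SD 1.25 and correlation 0.5, the difference is 1.2 − 0.5 = 0.7 and its SD is √(1.25² + 1.25² − 2 × 0.5 × 1.25²) = 1.25. Noncentrality is 1.77 and power is 0.35.
- With correlation 0 instead, the SD is 1.25 × √2 = 1.77, noncentrality is 1.25 and power is 0.20.

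Under (c) the effect therefore runs from none to large. The large end depends on the assumed pre-test mean of 0.5, for which the documents offer no support.

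**The case for a change.** The strongest case for acting is that the list directly follows the repeat rule, section 2.3 restates that rule without exception, and section 2.4 excludes no tool. Reading (a) does not rescue the paired test, because it leaves no baseline value to pair. Settling the matter would take a few sentences and one form with no added visit, and a baseline status that was never collected cannot be recovered.

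Part of this stands. The text does not choose between a change rating and a status rating, and section 2.4 cannot apply literally to a change rating taken only after baseline.

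The rest carries less weight. The data-loss argument needs a mismatch between intent and form, and the form is not in the documents; its items may already settle the question. That the result would be read beside the NIH Toolbox is a prediction, not something the plan proposes. The silence of section 2.4 on visits and scores applies to every outcome, so tool 5 is a small instance of a general brevity and not a contradiction of its own.

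**Conclusion.** The wording is ambiguous, but the concern does not call for a change. It is a gap that analysts would fill sensibly. Faced with change ratings from weeks 3 and 6, they would summarise them against no change; faced with status ratings from three visits, they would run the planned paired test. Only a pre-treatment change score subtracted from a later one causes damage, and nothing beyond list position points to it.

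The consequence is small. The self-assessment is in no hypothesis, and no primary or secondary conclusion rests on it. With 10 participants in a single-arm, open-label study it is descriptive whichever reading holds. The power figures above are illustrations on assumed values and carry no weight in this conclusion.

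The conclusion rests on two assumptions: that the form given to participants makes clear whether it asks about change or current state, and that the self-assessment stays a supporting measure, as section 2.2 implies. If it were promoted to an efficacy endpoint, its visits, scale and analysis would have to be written down.
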